3. PRÉCIS

There are approximately 46.8 million people worldwide affected by dementia with this number expected to double in the next 20 years. Dementia, the sixth leading cause of death within the United States, is a progressive and incurable condition that, unlike most other terminal illnesses, can have a disease course spanning several years. Unfortunately most persons living with dementia (PLWD) and their caregivers lack prognostic awareness coupled with the fact that capacity becomes compromised as the disease progresses results in these patients being at high risk for receiving aggressive and burdensome treatments at the end-of-life without clear associated improvements in quality of life or survival. Documented ACP can lead to increased treatment concordance with patient's wishes, as well as decreased hospitalization rates, in-hospital deaths, and overall healthcare costs. Despite these well-documented benefits, ACP has not been incorporated consistently into the care of community-dwelling older adults, particularly for PLWD. Most research on ACP has either excluded PLWD or has focused within the nursing home setting or in patients with advance stages of dementia; where most patients have limited capacity. Thus there is a critical need for ACP interventions that target PLWD early in the disease course and that involve their surrogate decision maker/caregiver to enhance goal-concordant care.

Past ACP interventions have primarily focused on the completion of advance directives. While completion of advanced directives may reduce over-treatment, it likely does not have a substantial impact on patient-centered care or satisfaction with care. ¹⁰ In a recent consensus statement on ACP, experts highlighted the identification and documentation of a surrogate decision-maker, discussion of values and care preferences with this surrogate, and documentation of these wishes in the EHR as the top 5 ACP patient-centered outcomes. ¹⁵ ACP interventions that include a focus on the communication of goals, values, and beliefs result in an increased receipt of goal-concordant care. ¹¹

Studies have shown that PLWD who complete ACP are less likely to want or receive aggressive interventions at the end of life. But possibly since dementia is under-recognized as a terminal condition and since capacity becomes compromised as the dementia progress, the rates of ACP completion remain low in this population. This is problematic since the lack of ACP is associated with increased rates of hospitalization, higher rates of tube feed insertions, higher healthcare cost, lower family satisfaction, and lower rates of hospice enrollment. Thus, there is growing recognition that improving goal-directed care in PLWD will require a greater focus on ACP early in the disease course for PLWD. Telehealth could play an integral role in promoting ACP implementation in PLWD and their caregivers but has been understudied in this population.

Telehealth has the potential to overcome barriers related to timing and travel restraints and to provide patients and their caregivers with an opportunity to discuss their goals, values, and priorities for their healthcare within their home setting. Recent studies have demonstrated patients' willingness to use telehealth and have shown that it can play an integral role in dementia care management.²⁷⁻³² However, the use of telehealth to conduct ACP has been understudied.³¹

The purpose of this study is to test a telehealth ACP intervention among patient-care partner dyads in those with either mild cognitive impairment (MCI), mild dementia, or unrecognized dementia. The goal is to evaluate the reach and adoption of ACP Telehealth intervention among those with either mild cognitive impairment, mild dementia, or unrecognized dementia.

3.1 Study Title

A Telehealth Advance Care Planning Intervention in those Patients with Mild Cognitive Impairment or Unrecognized Dementia.

3.2 Objectives/Aims

Aim 1: Evaluate the reach and adoption of a telehealth ACP intervention among patients with either mild cognitive impairment, mild dementia, or unrecognized dementia.

Aim 2: To evaluate the implementation of a telehealth ACP intervention by tracking the quality of ACP discussions documented within the EHR.

3.3 Design

This is a pragmatic pilot study where 300 patients with recognized or probable MCI or mild dementia and their care partner (if available) will be approached to participate in a telehealth ACP visit with a member of the patient's primary care team.

3.4 Interventions and Duration

One-time telehealth ACP visit with a primary care provider team member, the patient, and their care partner (optional). The visit will focus on disease understanding, prognosis (if appropriate), eliciting overall health-related goals and values, identification of meaning in life, unacceptable care states, the role of surrogate decision-maker, and end-of-life wishes.

3.5 Sample Size and Population

A sample size of 300 patients and their care partner (optional) with recognized or probable MCI or mild dementia.

In addition, up to 50 primary care providers who participated in our intervention will be approached to complete a RedCap survey at the end of the intervention.

6. STUDY OBJECTIVES

6.1 Primary Objective

Evaluate the reach and adoption of a telehealth ACP intervention among patients with either mild cognitive impairment, mild dementia, or unrecognized dementia.

H1: We hypothesize that at least 50% of 300 participants (N=100) will agree to participate and at least 90% of those who agree to participate (N=80) will complete the telehealth ACP intervention.

6.2 Secondary Objectives

To evaluate the implementation of the telehealth ACP intervention by tracking the quality of ACP discussions using an embedded EHR tool.

H2: We hypothesize that at least 80% of the completed telehealth ACP visits will be high-quality in nature. Discussion quality will be operationalized using a scoring system derived from the ACPWise documentation program.³⁶ High-quality ACP discussions will be defined as addressing ≥4 of the 9 core components in the ACP discussion: Disease understanding, health-related goals, what matters most in their life, important milestones, health-related worries, named surrogate decision-maker, unacceptable states at the end-of-life (e.g. being in a coma, etc.), goals if their health was to worsen, and documentation of code status.

7. BACKGROUND AND RATIONALE

7.1 Background on Condition, Disease, or Other Primary Study Focus

Dementia is a prevalent cause of death, despite low recognition as a terminal disease, is characterized by its indolent course. Given the limited prognostic awareness and compromised capacity that occurs as the disease progresses, persons living with dementia (PLWD) often undergo aggressive and burdensome treatments at the end of life. This makes PLWD an ideal population for early participation in Advance Care Planning (ACP). Documented ACP can lead to decreased hospitalization rates and inhospital deaths, decreased overall healthcare cost, and increases the likelihood of patients receiving medical care that is consistent with their overall goals, values, and health care preferences, i.e. goal-concordant care. Despite these well-documented benefits, ACP has not been incorporated consistently into the care of community-dwelling older adults, particularly for PLWD. Most research on ACP has excluded PLWD or has focused within the nursing home setting, where most patients have limited capacity. Thus there is a critical need for ACP interventions that target PLWD early in the disease course and that involve their surrogate decision-maker/caregiver to enhance goal-concordant care.

7.2 Rationale:

The COVID-19 pandemic has brought to the forefront the importance of ACP and the potential for coupling ACP with the use of telehealth to foster this important aspect of dementia care. ²⁷⁻³¹ Telehealth has the potential to overcome barriers related to timing and travel restraints and to provide patients and their caregivers with an opportunity to discuss their goals, values, and priorities for their healthcare within their home setting; prioritizing "aging in place". ³³ Telehealth has been proven to improve patient safety through the use of medication reminders, caregiver education support, and wandering-prevention tracking; and has led to decrease caregiver burden. ³³⁻³⁷ This highlighting the amenability of providing dementia care and management through telehealth. ³⁸ The COVID-19 pandemic also has addressed prior barriers related to reimbursement for telehealth services ³⁹, however, the use of telehealth for the purposes of ACP has been understudied. ³¹ The purpose of this study is to test a telehealth ACP intervention among patient-care partner dyads in those with either mild cognitive impairment (MCI) or unrecognized dementia. The goal is to evaluate the reach and adoption of ACP Telehealth intervention among those with either mild cognitive impairment, mild dementia, or unrecognized dementia.

8. STUDY DESIGN

8.1 Design:

This is a pragmatic pilot study where 300 patients with either mild cognitive impairment, mild dementia, or unrecognized dementia and their care partner will be approached to participate in a telehealth ACP visit with a member of their primary care team. Patients are still eligible to participate in the study even if a care partner/loved one does not attend the ACP visit with them. Our goal is to pilot-test and evaluate a pragmatic Telehealth ACP intervention among patients with either unrecognized dementia or with the diagnosis of mild cognitive impairment (MCI) or mild dementia.

8.2 Outcomes:

Primary outcomes: will be reach and adoption.

1. **Reach** will be defined as the proportion of eligible patient or patient-care partner dyads who agree

to participate.

2. Adoption will be defined as the proportion of patients or patient-care partner dyads who complete the ACP telehealth intervention.

Secondary outcomes:

1) Documented advance care planning discussion rates

- a) Documented in the ACPwise documentation template within the electronic health record.
- b) Reported as the number of discussed documented within the electronic health record. Completed determines better outcome.

2) Advance Care Planning Billing code usage

- a) ACP billing codes: 99497 and 99498 usages will be recorded.
- b) Usage of ACP Billing codes determines better outcome.

3) Quality of APC documentation

- a) Documented in the ACPwise documentation template within the electronic health record.
- b) Score of 0 (indicates no advance care planning questions answered) to 9 (indicates nine advance care planning questions answered)
- c) High-quality ACP discussions will be defined as addressing ≥4 of the 9 core components in the ACP discussion, with 1 point assigned if the following factors were addressed as part of the ACP discussion: Disease understanding, health-related goals, what matters most in their life, important milestones, health-related worries, named surrogate decision-maker, unacceptable states at the end-of-life (e.g. being in a coma, etc.), goals if their health was to worsen, and documentation of code status.

Exploratory Outcomes will include the estimated cost of delivering the intervention, the number of ACP visits completed with a care partner/loved one vs those without a care partner/loved one, the number of advance directives (AD) completed and uploaded into the EHR, and the rates of emergency room and inpatient hospitalizations. We will also survey PCPs and patient adopters to assess acceptability, appropriateness, and satisfaction with the intervention. Fidelity to the model will also be assessed by the number of times a patient had to be contacted prior to agreeing to participate, number of patients or patient-care partner dyads who do not show up to their Telehealth visit, the number of visits completed by telephone, and by video, the number of patients or patient-care partner dyads who have technological difficulty and are unable to be contacted for the visit via video, number of visits in which the ACPWise documentation tool was used by the PCP, and time lag between agreeing to participate and actually conducting their telehealth ACP visit. We will also examine the percentage that eRADAR identifies patients within the EHR who do or do not also have diagnostic codes for cognitive impairment.

8.3 Sample:

300 patients and their care partners (if available) will be approached for the study.

In addition, up to 50 primary care providers who participated in the study will be approached to complete a RedCap survey at the end of the intervention.

8.4 Setting:

Wake Forest Baptist Health, in collaboration with a physician-led group focused on value-based care

(CHESS Health Solutions), is affiliated with an ACO program that incorporates more than 150 primary care and multi-specialty practices with more than 330 physicians and Advanced Practice Providers in 80 locations in communities throughout central North Carolina. For this pilot project, participants will be recruited from 7 primary care clinics and an additional clinic will be added if needed to meet recruitment numbers

8.5 Study Duration:

One-time telehealth ACP visit with a member of the patient's primary care team.

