8.6 Intervention and Interactions

Patients

This is a pragmatic pilot study where 300 patients with either mild cognitive impairment, mild dementia, or unrecognized dementia and their care partners (if available) will be approached to participate in a telehealth ACP visit with a member of the patient's primary care team. Patients without willing or available care partners are still eligible to participate in the study. A list of eligible patients will be identified from the EHR using a combination of diagnosis codes and a novel risk prediction model for unrecognized dementia. The list will be provided to each corresponding site for the primary care physician to advise on the patient's capacity. Patients in which PCPs confirmed capacity will be approached first by the research team to gauge their interest in participating in the telehealth ACP visit. Patients will be asked if they have a care partner to join them in the visit. Depending on the patients' response, care partners' will be approached for participation. For patients and care partners that agree to participate, a dyad telehealth ACP visit will be scheduled. For patients who agree to participate but their care partners refused or patients who cannot identify a care partner to participate in the telehealth ACP visit, the visit will be scheduled only with the patient. Appointment information and reminders will be provided to the patient and care partner by mail, email, portal, telephone, and/or text messaging. Patients will be either be mailed (if we don't have a current email address or if patients prefer mail) or sent via email through RedCap an after-visit survey to assess patient's acceptability and appropriateness using the validated Acceptability of Intervention Measure (AIM)⁴⁰ and Intervention Appropriateness Measure (IAM)⁴⁰, and overall satisfaction with the intervention. For patients who either don't have current email address or prefer mail, a self-addressed stamped envelope will be provided for patients to mail back their survey. All patients who complete the survey will be entered into a raffle for a \$100 gift card.

Providers

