9. SELECTION AND ENROLLMENT OF PARTICIPANTS

Patients must reside in the state of NC and have seen their primary care provider within the past 12

months. In addition, patients must have recognized or probable MCI or mild dementia AND retain the decisional capacity to complete ACP. Patients will be identified through the EHR in one of two ways: (a) diagnosis codes (ICD-10) for MCI/Dementia or (b) the EHR Risk of Alzheimer's and Dementia Assessment Rule (eRADAR⁴¹) prediction model. The use of eRADAR will help to circumvent the reality that diagnostic codes for cognitive impairment are vastly underutilized; eRADAR utilizes dementia-related symptoms and risk factors as well as healthcare utilization from the EHR to identify patients with probable unrecognized dementia (a high likelihood of dementia/cognitive impairment in the absence of diagnosis codes). The research team will send PCPs the list of eligible patients before outreach to confirm that individuals still have capacity for decision-making.

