13.3 Data Analyses

The statistical approach for this project will be largely descriptive and focus on the estimation of key parameters for designing a subsequent embedded pragmatic clinical trial (ePCT). We've chosen to approach the primary outcomes for the pilot from a Bayesian paradigm, as it more naturally permits making probability statements concerning our criteria for adoption and the quality of ACP discussions (i.e. that at least 40% of approached patients will complete the telehealth ACP intervention, and that ≥80% of ACP discussion will be of high quality). Given that the primary endpoints are binary outcomes, we plan to use a standard conjugate Beta-Binomial hierarchical regression framework, which can accommodate covariates as needed. We expect that we will minimally evaluate variability in adoption by age, primary care practice / primary care provider, and by whether the patient was identified as having unrecognized dementia by the EHR Risk of Alzheimer's and Dementia Assessment Rule (eRADAR)⁴¹ or via diagnosis codes for MCI/ADRD.

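### Adoption, a primary outcome, has no stated denominator and two conflicting criteria (90% of those who agree, 40% of those approached), with neither said to govern

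*Combined protocol and SAP*

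**What the plan says.** Section 8.2, repeated in 13.2, defines the two primary outcomes. Reach "will be defined as the proportion of eligible patient or patient-care partner dyads who agree" to take part. Adoption "will be defined as the proportion of patients or patient-care partner dyads who complete the ACP telehealth intervention". The adoption sentence does not say whether the patients counted in the denominator are those listed, those approached or those who agreed.

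Two other places attach thresholds:

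- Section 6.1, H1, under the objective of evaluating reach and adoption. Its first clause, on agreement, reads "at least 50% of 300 participants (N=100) will agree to participate". Its second clause, on completion, takes a different base: "at least 90% of those who agree to participate (N=80) will complete the telehealth ACP intervention".
- Section 13.3, naming the criterion for adoption: "at least 40% of approached patients will complete the telehealth ACP intervention". The simulations in 13.1 use the same 40% threshold, applied to patients who consent and complete out of those approached.

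The word eligible is used in two ways. Section 8.6 says "A list of eligible patients will be identified from the EHR using a combination of diagnosis codes" and a prediction model, and section 9 says "The research team will send PCPs the list of eligible patients before outreach to confirm that individuals still have capacity for decision-making". Both apply the word before the capacity check. Yet PCP-confirmed capacity is itself an inclusion criterion (9.1), and 13.1 speaks of approaching 300 eligible patients.

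**The concern.** The pilot's stated purpose is to estimate parameters for a later pragmatic trial and to make probability statements about whether adoption reaches a threshold. A beta-binomial statement of that kind needs one defined binomial denominator and one threshold. For adoption the plan offers two of each and no order of precedence. If the choice is made after the counts are known, the feasibility conclusion on a primary outcome becomes discretionary.

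H1's printed counts give no help in deciding, because they do not match the percentages beside them. For reach, the definition relies on a word that the protocol also applies to a wider group than the one telephoned, and no rule covers patients who are never reached.

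**Working it through.** **Inputs.** H1 thresholds (50%, 90%) and counts (100, 80) from 6.1; the 40% threshold from 13.1 and 13.3; the number approached, 300 (3.3, 8.1, 8.3 and 13.1) or 200 (opening sentence of 13.1); the prior Beta(14.4, 16.0) and the expected completers, median 94 (quartiles 81 and 108), from 13.1.

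**1. The plan's own figures.** The prior reproduces: mean 14.4/30.4 = 47.4%, quartiles 41% and 53%. The beta-binomial prediction of completers gives:

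- 300 approached: median 142, quartiles 123 and 161. This does not match the stated 94 (81, 108).
- 200 approached: median 95, quartiles 82 and 108. This matches to within one patient.

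The share 94/200 is 47%, in line with the prior, whereas 94/300 is 31%, below the 40% criterion. In 13.1, then, adoption is completed over approached, and the printed completer counts belong to 200.

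**2. H1's printed counts.**

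- 50% of 300 = 150, not 100. The printed 100 is 50% of 200.
- 90% of 100 = 90, not 80. The printed 80 is 80/100 = 80% of those agreeing.
- 80/200 = 40%, and 80/300 = 26.7%.

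The printed 80 is thus consistent with the 40% rule at 200 approached, although it stands beside the 90% rule.

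**3. Can the criteria disagree?** Let A be approached, g agreeing and c completing. H1 requires g/A ≥ 0.50 and c/g ≥ 0.90. The other criterion requires c/A ≥ 0.40.

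- *40% rule met, H1 missed.* A = 300, g = 150, c = 125. Reach is 150/300 = 50%, which meets H1's first part. Then c/A = 125/300 = 41.7% (met) and c/g = 125/150 = 83.3% (missed). The posterior probability that adoption is at least 40% is 0.79 with the stated prior and 0.72 with a Jeffreys prior. With 150 agreeing, the 40% rule needs 0.40 × 300 = 120 completers and the 90% rule needs 0.90 × 150 = 135, so any count from 120 to 134 gives this split on the observed proportions.
- *H1 met, 40% rule missed.* This cannot happen. If both parts of H1 hold, c/A = (g/A) × (c/g) ≥ 0.50 × 0.90 = 0.45.
- *90% clause met alone, 40% rule missed.* A = 300, g = 130, c = 119. Here c/g = 91.5% and c/A = 39.7%. But g/A = 43.3%, so H1 has already failed on reach.

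**4. Reach.** H1 divides by 300, and 13.1 equates the 300 approached with eligible patients. The definition in 8.2 and 13.2 says only eligible. The size of the EHR list is not given. As an assumption, with a list of 350 to 400 and 150 agreeing, reach would be 150/350 = 42.9% to 150/400 = 37.5% of the list, against 50% of those approached. This shows why the term should be defined. It is not a forecast.

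**The case against.** **Each threshold carries its own base.** H1's second clause could be read as visit completion and the 40% figure as the adoption rule, with no conflict. That is a sensible way to resolve it, and the fix below adopts it. But the plan does not say so: H1 is the only hypothesis under the objective of evaluating reach and adoption, and 13.3 gives a different adoption criterion without referring to H1.

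**The pilot is largely descriptive.** The tracking log records ineligibility, non-participation and acceptance, and no-shows are counted, so most alternative ratios could be reported anyway. This stands, and it limits the harm to an unclear feasibility conclusion. Inflated type I error is not at issue.

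**Stronger readings that the documents do not support.**

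- A reader might infer that reach is to be divided by the whole EHR list. Capacity confirmed by the PCP is an inclusion criterion, 13.1 speaks of approaching 300 eligible patients, and H1 tests reach against 300. No criterion is set against the list.
- A reader might infer that patients whose PCP does not reply are listed but never approached. The documents do not discuss PCP non-response, and 8.6 says only that "Patients in which PCPs confirmed capacity will be approached first by the research team".
- A reader might infer that unreached patients will be dropped, inflating reach. Nothing says they will be. The rule is simply absent.
- A reader might infer that H1 and the 40% rule can split in either direction. Step 3 shows that they cannot, unless the 90% clause is read alone.

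**Conclusion.** The point holds for adoption on the text alone. A primary outcome has no denominator where it is defined, two criteria on different bases elsewhere, and no statement of which governs. With 300 approached and 150 agreeing, any number of completers from 120 to 134 meets the 40% rule and misses H1. This needs no assumption beyond the hypothetical counts. The split between full H1 and the 40% rule runs in that one direction.

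H1's counts of 100 and 80 are inconsistent with its own 300 and 90%. They fit 200 approached, as do the expected completers in 13.1.

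For reach, the finding is smaller: the word eligible and the handling of unreached patients need defining. Any figure for reach over the EHR list rests on an assumed list size. This should be corrected because it determines how the main feasibility conclusion is drawn, and the correction is cheap.

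**What to change.** In 6.1, 8.2, 13.2 and 13.3:

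- Define adoption as patients completing the visit / patients approached, with the 40% criterion governing, as in 13.1 and 13.3.
- Report completed / agreed separately as visit completion, with 90% as a secondary target.
- Define reach as patients agreeing / the same approached set. Count patients, so that a dyad counts once.
- State that eligible means PCP-confirmed capacity, and keep patients never reached by telephone in the denominator. State also how patients found to lack capacity at or after contact (9.3) are counted.
- Reconcile the 200 and 300 in 13.1 and restate H1's counts for the number chosen. For 300, 50% agreeing is 150 and 40% completing is 120. For 200 they are 100 and 80. Recompute the expected completers in 13.1 to match.

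Agreed / EHR-listed can be added as an optional descriptive figure. The cost is protocol and SAP wording, and the tracking log already collects most of what is needed. The downside is that reported rates may look slightly less favourable.
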